### **Data Safety Monitoring Plan:**

#### **1. Personnel responsible for the safety review and its frequency:**

The principal investigator will be responsible for monitoring the data, assuring protocol compliance, and conducting the safety reviews at the specified frequency which must be conducted at a minimum of every 6 months (including when re-approval of the protocol is sought). During the review process, the principal investigator (monitor) will evaluate whether the study should continue unchanged, require modification/amendment, or close to enrollment. Either the principal investigator, the IRB or Safety Monitoring Committee (DSMC) have the authority to stop or suspend the study or require modifications.

#### **2. The risks associated with the current study are deemed moderate for the following reasons:**

1. We do not view the risks associated with the radiotracer [11C]PHNO as minimal.
2. We do not view the risks associated with the combined use of \_\_\_\_\_ and \_\_\_\_\_ as minimal.
3. Given the now established safety and validity of the current \_\_\_\_\_ in our prior work, we do not view the proposed studies as high risk.
4. Given our experience with the combined co-administration \_\_\_\_\_, we do not view the proposed studies as high risk.

Although we have assessed the proposed study as one of moderate risk, the potential exists for anticipated and/or unanticipated adverse events, serious or otherwise, to occur since it is not possible to predict with certainty the absolute risk in any given individual or in advance of first-hand experience with the proposed study methods. Therefore, we provide a plan for monitoring the data and safety of the proposed study as follows:

#### **3. Attribution of Adverse Events:**

Adverse events will be monitored for each subject participating in the study and attributed to the study procedures / design by the principal investigator [name]. according to the following categories:

- a.) Definite: Adverse event is clearly related to investigational procedures(s)/agent(s).
- b.) Probable: Adverse event is likely related to investigational procedures(s)/agent(s).
- c.) Possible: Adverse event may be related to investigational procedures(s)/agent(s).
- d.) Unlikely: Adverse event is likely not to be related to the investigational procedures(s)/agent(s).

e.) Unrelated: Adverse event is clearly not related to investigational procedures(s)/agent(s).

#### **4. Plan for Grading Adverse Events:**

The following scale will be used in grading the severity of adverse events noted during the study:

1. Mild adverse event
2. Moderate adverse event
3. Severe

#### **5. Plan for Determining Seriousness of Adverse Events:**

##### **Serious Adverse Events:**

In addition to grading the adverse event, the PI will determine whether the adverse event meets the criteria for a Serious Adverse Event (SAE). An adverse event is considered serious if it:

1. is life-threatening OR
2. results in in-patient hospitalization or prolongation of existing hospitalization OR
3. results in persistent or significant disability or incapacity OR
4. results in a congenital anomaly or birth defect OR
5. results in death OR
6. based upon appropriate medical judgment, may jeopardize the subject's health and may require medical or surgical intervention to prevent one of the other outcomes listed in this definition, OR
7. adversely affects the risk/benefit ratio of the study

An adverse event may be graded as severe but still not meet the criteria for a Serious Adverse Event. Similarly, an adverse event may be graded as moderate but still meet the criteria for an SAE. It is important for the PI to consider the grade of the event as well as its "seriousness" when determining whether reporting to the HIIRB is necessary.

#### **6. Plan for reporting serious AND unanticipated AND related adverse events, anticipated adverse events occurring at a greater frequency than expected, and other unanticipated problems involving risks to subjects or others to the IRB**

The investigator will report the following types of adverse events to the IRB: a) serious AND unanticipated AND possibly, probably or definitely related events; b) anticipated adverse events occurring with a greater frequency than expected; and c) other unanticipated problems involving risks to subjects or others.

These adverse events or unanticipated problems involving risks to subjects or others will be reported to the IRB within 48 hours of it becoming known to the investigator, using the appropriate forms found on the website.

#### **7. Plan for reporting adverse events to co-investigators on the study, as appropriate the protocol's research monitor(s), e.g., industrial sponsor, Yale Cancer Center Data and Safety Monitoring Committee (DSMC), Protocol Review Committee (PRC), DSMBs, study sponsors, funding and regulatory agencies, and regulatory and decision-making bodies.**

For the current study, the following individuals, funding, and/or regulatory agencies will be notified:

- All Co-Investigators listed on the protocol.
- Safety Monitoring Committee (DSMC)
- National Institutes of Health

The principal investigator [name]. will conduct a review of all adverse events upon completion of every study subject. The principal investigator will evaluate the frequency and severity of the adverse events and determine if modifications to the protocol or consent form are required.

**11. Statistical Considerations:** Describe the targeted number of subjects and the statistical analyses that support the study design.

Demographics between smokers and nonsmokers will be compared using *t* tests or Chi-Square tests, as appropriate. Scores on psychological tests such as depressive symptoms at baseline will be compared between groups and may be used as covariates in subsequent analyses. All outcomes will be summarized descriptively and assessed for normality prior to analysis using normal probability plots and Kolmogorov test statistics. Transformations or nonparametric analyses will be performed as necessary. All tests will be two-sided and considered statistically significant at  $\alpha = 0.05$ . Post-hoc comparisons will be conducted as necessary with significance levels adjusted for multiple comparisons basing the adjustment on the number of conceptually related statistical tests within each hypothesis. All statistical analyses will be conducted using SAS version 9.3 (Cary, NC).

**Aim 1. To determine if amphetamine-induced DA release is blunted during abstinence in tobacco smokers compared to nonsmokers.** Hypothesis 1. We hypothesize that amphetamine-induced striatal DA release will be blunted in smokers compared to nonsmokers. Power Calculations for Hypothesis 1: Our preliminary data revealed blunted amphetamine-induced DA release ( $d=0.91$ ) in the ventral striatum among smokers ( $-21\% \pm 12.0$ ) compared to nonsmokers ( $-29\% \pm 6.3$ ). Assuming a two-sided t-test with  $\alpha=0.05$ , 40 nonsmokers and 50 smokers assessed after 14-21 days of abstinence will provide 80% statistical power to detect effect sizes as small as  $d=0.63$ , which compares favorably with the effects observed above.

Regional [ $^{11}\text{C}$ ]PHNO uptake for each subject will be quantified as  $\text{BP}_{\text{ND}}$  described above for each ROI and will represent the primary outcome measure for the proposed experiments. Repeated measures ANOVA will be used to evaluate the change between scans ( $\Delta\text{BP}$ ) for brain measures for the scans.  $\Delta\text{BP}$  will be computed as  $[(\text{BP}_{\text{baseline}} - \text{BP}_{\text{condition}}) / \text{BP}_{\text{baseline}} \times 100]$ . Analysis will be conducted using SAS version 9.1 (Cary, NC).  $N=20$  subjects per group is necessary to detect differences between smokers and nonsmokers. Potential associations, e.g., relationship between magnitude of dopamine release and time to relapse, will be examined using correlation analysis with Type I error corrected for multiple comparisons. Exploratory analyses of the other cognitive and behavioral measures and their relationship to relapse will also be performed.

**SECTION III: RESEARCH INVOLVING DRUGS, BIOLOGICS, RADIOTRACERS, PLACEBOS AND DEVICES**

*If this section (or one of its parts, A or B) is not applicable, state N/A and delete the rest of the section.*

**DRUGS, BIOLOGICS and RADIOTRACERS**

**12. Identification of Drug, Biologic or Radiotracer:** What is (are) the **name(s)** of the drug(s), biologic(s) or radiotracer(s) being used? Identify whether FDA approval has been granted and for what indication(s).

[C]PHNO, IV, radioactivity dose of no more than 10 millicuries for one injection. [C]PHNO has been used in humans and has been shown to be *safe and well tolerated after its administration to healthy subjects or patients*. No serious adverse effects are expected from tracer doses, which is one thousand fold  $\leq$  the pharmacological used during the therapeutic trials of PHNO. This will be used under the PET Center's approved IND#**134138** for the radiotracer [C]PHNO.

**d-Amphetamine**, dose 0.5 mg/kg, PO by study physician to participants so no IND necessary per 21 CFR 312.2(b).

All protocols which utilize a drug, biologic or radiotracer **not** approved by, but regulated by, the FDA must provide the following information:

- a. What is the Investigational New Drug (IND) **number** assigned by the FDA? 134138
- b. Who holds the IND? Yale PET Center
- c. All protocols which utilize a radiotracer not approved by, but regulated by the FDA must provide the IND number:  
Alternatively, use of the investigational radiotracer may be under RDRC/RSC oversight: (check if appropriate) \_\_\_\_\_

For all investigational radiotracers, attach a copy of the RDRC/RSC application ( for radioisotopes used in the PET Center, PET Center personnel may complete this step) Go to <http://rsc.med.yale.edu/login.asp?url=myApps.asp>. When you have logged in, complete the application and attach a copy to this submission.

Alternatively, an **exemption from IND filing requirements** may be sought for a clinical investigation of a drug product that is lawfully marketed in the United States. If there is no IND and an exemption is being sought, review the following categories and complete the category that applies

(and delete the inapplicable categories):

### Exempt Category 1 (d-Amphetamine)

The clinical investigation of a drug product that is lawfully marketed in the United States can be exempt from IND regulations if all of the following are yes:

- i. The intention of the investigation is NOT to report to the FDA as a well-controlled study in support of a new indication for use or to be used to support any other significant change in the labeling for the drug.  Yes  No
- ii. The drug that is undergoing investigation is lawfully marketed as a prescription drug product, and the intention of the investigation is NOT to support a significant change in the advertising for the product.  Yes  No
- iii. The investigation does NOT involve a route of administration or dosage level or use in populations or other factor that significantly increases the risks (or decreases the acceptability of the risks) associated with the use of the drug product.  Yes  No
- iv. The investigation will be conducted in compliance with the requirements for institutional (HIC) review and with the requirements for informed consent of the FDA regulations (21 CFR Part 50 and 21 CFR Part 56).  Yes  No
- v. The investigation will be conducted in compliance with the requirements regarding promotion and charging for investigational drugs.  Yes  No

### Exempt Category 2 (all items i, ii, and iii must be checked to grant a category 2 exemption)

- i. The clinical investigation is for an *in vitro* diagnostic biological product that involves one or more of the following (check all that apply):
- Blood grouping serum
  - Reagent red blood cells
  - Anti-human globulin
- ii. The diagnostic test is intended to be used in a diagnostic procedure that confirms the diagnosis made by another, medically established, diagnostic product or procedure; and
- iii. The diagnostic test is shipped in compliance with 21 CFR §312.160.

### Exempt Category 3

- The drug is intended solely for tests in vitro or in laboratory research animals if shipped in accordance with 21 CFR 312.60

### Exempt Category 4

- A clinical investigation involving use of a placebo if the investigation does not otherwise require submission of an IND.

1. **Background Information:** Provide a description of previous human use, known risks, and data addressing dosage(s), interval(s), route(s) of administration, and any other factors that might influence risks. If this is the first time this drug is being administered to humans, include relevant data on animal models.

**Previous human use of [C]PHNO**

The use of [C]PHNO in PET imaging in human was first reported in 2006 (37). No relevant abnormalities in blood pressure, heart rate, or ECG were reported at any time in the study. There also were no relevant findings in physical or neurological exams or in routine blood and urine analyses during the study. However nausea was reported approximately 2–3 min after tracer injection, which subsided rapidly 2–3 min later. This effect was attributed to the transient high [C]PHNO concentration resulting from the bolus injection may have been responsible for the reported transient self-limiting nausea (37).

[C]PHNO has been extensively used in many clinical trials. A survey of the *ClinicalTrials.gov* website shows 12 completed trials, 5 recruiting trials, and 1 active clinical trial with [C]PHNO investigating a variety of behaviors and disorders: alcohol drinking, addictive behavior, behavioral symptoms, cocaine-related disorders, compulsive behavior, depression, depressive disorder, drinking behavior, impulsive behavior, mental disorders, mood disorders, obsessive-compulsive disorder, psychotic disorders, schizophrenia studies, schizophrenia spectrum and other psychotic disorders, psychological stress, substance-related disorders, and tobacco use disorder.

[C]PHNO has been used in humans at the Yale University PET center in several studies including HIC 0910005822. To date, more than 250 human [C]PHNO scans have been conducted at Yale PET Center. All injected doses were limited to  $\leq 0.03 \mu\text{g}/\text{kg}$ . These studies included smokers, cocaine users, pathological gamblers, schizophrenia subjects, and healthy controls. Adverse events were observed in studies which involved administration of amphetamine in addition to [C]PHNO. The typical protocol involved a morning [C]PHNO administration, followed by oral amphetamine, followed by a second PHNO injection, starting 3 hours post-amphetamine. Because nausea is attributed to the transient high [C]PHNO concentration 2–3 min after the bolus injection of the tracer (37), the Yale PET Center administers [C]PHNO as a bolus over a period of 5 minutes, *i.e.*, at a PHNO dose rate of 7 ng/min for the average 70 kg subject. Administration of [C]PHNO dose at this rate is about 5 times slower than lowest rate reported in the clinical study involving i.v. administration of PHNO (38).

**Proposed single study dose limit**

[C]PHNO will be administered intravenously.

The proposed radioactivity dose of 10 mCi per single administration is below the 21 CFR 361.1 estimated dose limit of 75.5 mCi for a 70 kg Hermaphrodite Male (77.7 mCi for female). The estimated dose limit calculations are based upon the liver as the critical organ; 5 rem per single study limit: 0.0662 rem per mCi to the combined male and female livers.

The maximum allowable dose for a single injection is 3000 mR to the whole body, active blood-forming organs, lens of the eye and gonads. The dose to any other organ cannot exceed 5000 mR.

The maximum allowable dose for one year is 5000 mR to the whole body, active blood-forming organs, lens of the eye and gonads. The dose to any other organ cannot exceed 15000 mR.

For comparison, the average person in the United States receives a radiation exposure of 0.3 rem (or 300 mrem) per year from natural background sources, such as from the sun, outer space, and from radioactive materials that are found naturally in the earth's air and soil. The dose that a subject will receive from participation in this research study would be less than that obtained in one year from natural sources.

As previously mentioned, the maximum amount of radiation per year an individual subject will receive in this study is from up to 8 injections of  $\leq 10\text{mCi}$  each of  $[^{11}\text{C}]\text{PHNO}$ , plus transmission scans. The intended amount is from up to 4 injections of  $\leq 10\text{mCi}$  each of  $[^{11}\text{C}]\text{PHNO}$  for smokers and up to 2 injections of  $\leq 10\text{mCi}$  each of  $[^{11}\text{C}]\text{PHNO}$  in nonsmokers, however in case of scan failures post injection we have included up to 8 injections if scan sets need to be repeated within the study time frame (i.e. 1-2 wks withdrawal and 2-8 wks withdrawal). Nonsmokers maximum number of injections including re-scans would be 4 scans total. Should the second scan of the set fail, we will make every effort to reschedule the scan for repeat within 1 wk, however if scheduling does not permit this, we may ask the subject to repeat the whole set due to timing related data.

2 injections PHNO	0.4292 rem
4 injections PHNO	0.8584 rem
8 injections PHNO	1.7168 rem

d-Amphetamine:

Amphetamine is administered to measure changes in  $[^{11}\text{C}]\text{PHNO}$  binding due to dopamine release. This dose was chosen because it is expected to produce a quantifiable displacement of the radiotracer. The risks are outlined in Section VI. Oral and IV d-amphetamine administration to healthy humans and individuals with psychiatric disorders has been safely used in many PET imaging studies. We will use the oral route due to the greater safety and ease of administration.

3. **Source:** a) Identify the source of the drug or biologic to be used.

$[^{11}\text{C}]\text{PHNO}$  will be synthesized at the Yale University PET Center radiochemistry Laboratory under the supervision of Drs. [name] & [name].

d-amphetamine will be provided by the YNHH pharmacy.

- b) Is the drug provided free of charge to subjects?  Yes  No  
If yes, by whom? PET center

4. **Storage, Preparation and Use:** Describe the method of storage, preparation, stability information, and for parenteral products, method of sterilization and method of testing sterility and pyrogenicity.

$[^{11}\text{C}]\text{PHNO}$

Due to the short half-life, PET drugs are prepared and formulated immediately before administration, and therefore there are no issues with storage or stability. PET drug products are stored at room temperature and are stable for at least 60 min after preparation.

The preparation of sterile PET drug products is validated prior to human use. Sterility is achieved by passing the PET drug product through a 0.22 micron membrane filter during the last step of the formulation process. Prior to release for administration, a bubble point test is performed on the membrane filter used for terminal sterilization in order to validate and verify its integrity during the filtration process. Due to the short half-life, a sample of the PET drug product is tested for sterility after administration for further confirmation.

The level of endotoxin in each batch of the final PET drug product is determined quantitatively prior to release for administration using the FDA approved Charles River Laboratory's Portable Testing System (Endosafe®-PTS).

[C]PHNO will be prepared at the Yale PET Center in accordance with local Chemistry Manufacturing & Control (CMC) procedures and quality specifications described in local FDA-approved Drug Master File (IND No. 134138). Briefly, [C]propionyl chloride is prepared by reaction of [C]CO2 with ethylmagnesium bromide, followed by treatment with phthaloyl dichloride. [C]propionyl chloride then reacts with 9-hydroxynaphthoxazine to generate a [C]-amide, which is subsequently reduced by lithium aluminium hydride to yield [C]PHNO. The resulting PET drug product is purified first by semi-preparative HPLC, followed by solid-phase extraction to remove the HPLC buffer mixture. Finally [C]PHNO is formulated in <10% ethanolic saline solution (USP), and the resulting PET drug product is then passed through a 0.22 micron sterile membrane filter for terminal sterilization and collected in a sterile pyrogen free collection vial to afford a formulated I.V. solution ready for dispensing and administration.

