### **1. Risks Associated with Radiation**

The Yale University Radioactive Drug Research Committee (YURDRC) will review the use of radiation in this research study, and no subjects will be enrolled until RDRC approval is obtained. This research study involves exposure to radiation from [F]NCFHEB and [C]PHNO PET scanning. This radiation exposure is not necessary for medical care and is for research purposes only.

For each individual [F]NCFHEB PET scan, subjects will receive up to  $\leq 8$  mCi of [F]NCFHEB, plus transmission scans. This is equal to an effective dose equivalent of 0.635 rem per injection. For each individual [C]PHNO PET scan, subjects will receive up to  $\leq 10$  mCi of [C]PHNO, plus transmission scans. This is equal to an effective dose equivalent of 0.27 rem per injection.

The maximum amount of radiation per year an individual subject will receive in this study is from up to 4 injections of  $\leq 8$  mCi each of [F]NCFHEB, up to 2 injections of  $\leq 10$  mCi each of [C]PHNO, plus transmission scans. This includes the fact that some subjects may have to come back on a separate day for baseline and physostigmine scans. Four [F]NCFHEB injections and two [C]PHNO injections is the maximum each subject may receive from participation in this study.

Although each organ will receive a different dose, the maximum amount of radiation exposure subjects will receive per year from this study is equal to an effective dose equivalent of 3.08 rem for a total of up to 32 mCi of [F] NCFHEB in 4 injections of  $\leq 8$  mCi each and 20 mCi of [C] PHNO in 2 injections of  $\leq 10$  mCi each. This calculated value is used to relate the dose received by each organ to a single value.

The amount of radiation subjects will receive in this study is below the dose guidelines established by the FDA and monitored by the Yale University Radioactive Drug Research Committee for research subjects. This guideline sets an effective dose limit of 5 rem per year.

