## 2.2. Dosimetry Studies of [ $^{11}\text{C}$ ]PHNO in Monkeys at Yale PET Center

Radiation dosimetry for [ $^{11}\text{C}$ ]PHNO has been estimated (using the standard MIRD absorption fractions program MIRDOSE 3.1) based on PET scans with a tracer dose of [ $^{11}\text{C}$ ]PHNO on four Rhesus monkeys (2 females and 2 males) to obtain organ concentration and residence time. The percentage of the injected dose per  $\text{cm}^3$  was calculated from ROIs drawn on the PET images, and average organ weights for female and male Rhesus monkeys were used to derive the amount of activity per organ as a function of time. The scans were carried out to 120 minutes and the residence times calculated from a trapezoidal approximation of the integral.

Based on these numbers we estimated that the maximum allowable injection dose for [ $^{11}\text{C}$ ]PHNO is 55 mCi per single injection. We tabulated the dosimetry below (all entries refer to scan data from monkeys).

	Absorbed Dose (rad/mCi)		max rad/study	RDRC MAX DOSE
	mean	SD		
Brain	1.84E-02	2.08E-03	5	2.72E+02
Breasts	6.64E-03	4.08E-04	5	7.53E+02
Gallbladder Wall	4.63E-02	2.66E-02	5	1.08E+02
LLI Wall	9.72E-03	4.12E-04	5	5.14E+02
Small Intestine	2.95E-02	4.77E-03	5	1.70E+02
Stomach Wall	1.32E-02	2.45E-03	5	3.80E+02
ULI Wall	1.20E-02	4.11E-04	5	4.18E+02
Heart Wall	1.43E-02	1.26E-03	5	3.50E+02
Kidneys	9.07E-02	2.83E-02	5	5.51E+01

Liver	5.56E-02	9.17E-03	5	9.00E+01
Lungs	2.86E-02	7.17E-03	5	1.75E+02
Muscle	7.79E-03	4.49E-04	5	6.42E+02
Ovaries	1.06E-02	4.24E-04	5	4.73E+02
Pancreas	3.21E-02	7.45E-03	3	9.34E+01
Red Marrow	1.10E-02	5.45E-04	5	4.57E+02
Osteogenic Cells	1.23E-02	6.85E-04	3	2.43E+02
Skin	5.89E-03	5.34E-04	5	8.49E+02
Spleen	1.71E-02	3.81E-03	5	2.92E+02
Testes	7.03E-03	6.25E-04	5	7.11E+02
Thymus	7.77E-03	4.70E-04	3	3.86E+02
Thyroid	6.90E-03	7.79E-04	5	7.25E+02
Urinary Bladder Wall	7.01E-02	1.88E-02	5	7.13E+01
Uterus	1.37E-02	2.32E-03	5	3.65E+02
Total Body	1.04E-02	0.00E+00	5	4.81E+02
Effective Dose Equivalent	2.69E-02	4.72E-03		
Effective Dose (rem/mCi)	1.92E-02	2.57E-03	Critical organ	Max Dose (mCi)
ED with Stom Adjust	2.08E-02	2.81E-03	Kidneys	5.51E+01

The maximum allowable dose for a single injection is 3000 mR to the whole body, active blood-forming organs, lens of the eye and gonads. The dose to any other organ cannot exceed 5000 mR.

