**1. Risks Associated with Radiation**

The Yale New Haven Radiation Safety Committee and the FDA will review the use of radiation in this research study as the radiotracer [C]PHNO PET will be under IND # **134138**, This research study involves exposure to radiation from [C]PHNO PET scanning. This radiation exposure is not necessary for medical care and is for research purposes only.

For each individual [C]PHNO PET scan, subjects will receive up to ≤ 10 mCi of [C]PHNO, plus transmission scans. This is equal to an effective dose equivalent of 0.2146 rem per injection.

The maximum amount of radiation per year an individual subject will receive in this study is from up to 8 injections of ≤ 10mCi each of [C]PHNO, plus transmission scans. The intended amount is from up to 4 injections of ≤ 10mCi each of [C]PHNO for smokers and up to 2 injections of ≤ 10mCi each of [C]PHNO in nonsmokers, however in case of scan failures post injection we have included up to 8 injections if scan sets need to be repeated within the study time frame (i.e. 1-2 wks withdrawal and 2-8 wks withdrawal). Nonsmokers maximum number of injections including re-scans would be 4 scans total. Should the second scan of the set fail, we will make every effort to reschedule the scan for repeat within 1 wk, however if scheduling does not permit this, we may ask the subject to repeat the whole set due to timing related data.

Although each organ will receive a different dose, the maximum intended amount of radiation exposure subjects will receive per year from this study is equal to an effective dose equivalent of 0.858400001 rem for a total of up to 40 mCi of [C] PHNO in 4 injections of ≤ 10mCi each for smokers and 0.4292 rem for a total of up to 20 mCi [C] PHNO in 2 injections of ≤ 10mCi each for non smoker. This calculated value is used to relate the dose received by each organ to a single value.

However, if scans should need to be repeated the maximum dose for smokers would be equal to an effective dose of 1.716800002 rem from up to 8 injections and for non smokers would be 0.858400001 rem from up to 4 injections. We have every intention to limiting radiation exposure to subjects and avoiding re-scans if possible.

2 injections PHNO	0.4292 rem
-------------------	------------

4 injections PHNO	0.8584 rem
8 injections PHNO	1.7168 rem

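### The PHNO protocol says that taking part gives less radiation than a year of natural background (0.3 rem), but its own table gives up to 1.4 times that for the smallest planned participation

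*Combined protocol and SAP*

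**What the plan says.** The file holds two protocols, one for [18F]NCFHEB and one for [11C]PHNO.

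**PHNO protocol.** Section III, Proposed single study dose limit, gives natural background as 0.3 rem per year and says that the dose "from participation in this research study would be less than that obtained in one year from natural sources". The next paragraph and the closing table set out the injections and totals for the study. On the ceiling for controls it says: "Nonsmokers maximum number of injections including re-scans would be 4 scans total".

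Item 9, Risks Associated with Radiation, puts 0.2146 rem on each injection of up to 10 mCi and assigns the totals to groups:

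- nonsmokers as intended: "0.4292 rem for a total of up to 20 mCi";
- nonsmokers with repeat scans: "for non smokers would be 0.858400001 rem from up to 4 injections";
- smokers as intended: "effective dose equivalent of 0.858400001 rem for a total of up to 40 mCi";
- smokers with repeat scans: "the maximum dose for smokers would be equal to an effective dose of 1.716800002 rem from up to 8 injections".

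**NCFHEB protocol.** The same comparison closes the section on PHNO dosimetry in monkeys. That section covers PHNO only and works per injection; for example, it estimates that the maximum allowable PHNO dose "is 55 mCi per single injection". In the risk section of this protocol, the sentence on each PHNO scan reads: "This is equal to an effective dose equivalent of 0.27 rem per injection". The figure there for each NCFHEB injection is 0.635 rem.

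**The concern.** In the PHNO protocol, the comparison and the numbers that refute it stand under one heading. The sentence speaks of taking part in the study, and the study is never planned as one injection: nonsmokers have one set of two scans, and smokers have one set with the option of a second. If the table is right, the sentence is wrong for every planned participant scanned at the permitted activity.

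What is at stake is the accuracy of a risk statement about volunteers in a document written for ethics review. The exposure is for research purposes only, and nonsmokers get no direct benefit. The error runs in the reassuring direction, and a comparison with background is easier to remember, and to reuse in other text, than a table in rem.

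**Working it through.** **Inputs**

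- Background: 0.3 rem per year (both protocols, next to the sentence).
- PHNO protocol: 0.2146 rem per injection of up to 10 mCi (item 9, Risks).
- NCFHEB protocol: 0.27 rem per PHNO injection and 0.635 rem per NCFHEB injection (item 9, Risks). From the PHNO dosimetry table, per mCi: effective dose equivalent 0.0269, effective dose 0.0192 rem, total body 0.0104 rad.

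**Step 1. Reproduce the PHNO protocol's totals.** Total = number of injections × 0.2146.

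- 2 × 0.2146 = 0.4292 rem
- 4 × 0.2146 = 0.8584 rem
- 8 × 0.2146 = 1.7168 rem

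All three match the table, so the totals contain no arithmetic error.

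**Step 2. Compare with one year of background.** Multiple = total / 0.3.

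| Injections | Who | Ceiling (rem) | Multiple of 0.3 rem |
|---|---|---|---|
| 1 | no planned participation | 0.2146 | 0.72 |
| 2 | nonsmokers as intended; smoker with one set | 0.4292 | 1.43 |
| 4 | smokers as intended; nonsmokers with repeat scans | 0.8584 | 2.86 |
| 8 | smokers with both sets fully repeated | 1.7168 | 5.72 |

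Only a single injection is below background. Every total is below the 5 rem annual limit.

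**Step 3. How low would the activity have to be?** The figures are ceilings. Assuming that dose scales with injected activity, one mCi carries 0.2146 / 10 = 0.02146 rem, and 0.3 / 0.02146 = 13.98 mCi in total reaches background. Two injections would have to stay under about 7.0 mCi each (13.98 / 2), and four under about 3.5 mCi each (13.98 / 4). The protocol sets only the 10 mCi cap.

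**Step 4. The instance in the NCFHEB protocol.**

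- One PHNO injection: 10 × 0.0269 = 0.269, stated as 0.27 rem; 0.27 / 0.3 = 0.90. On this reading the sentence is true.
- One NCFHEB scan: 0.635 / 0.3 = 2.12. Read as taking part in the study, the sentence is false after a single NCFHEB scan at permitted activity.
- Two PHNO injections at 10 mCi, by metric: effective dose equivalent 2 × 0.27 = 0.54 rem; effective dose 2 × 10 × 0.0192 = 0.384 rem; total body 2 × 10 × 0.0104 = 0.208 rad. If rad and rem are taken as equal here (an assumption) and transmission scans are left out, the last is below 0.3.

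**The case against.** **The sentence was meant per injection.** The heading in the PHNO protocol refers to a single-study limit, the section opens with the activity per administration, and one injection is indeed below 0.3 rem. A comparison left over from per-injection text is a plausible origin. That explains the wording but does not correct it: the sentence names participation in the study, follows the one-year limit, and is followed by a paragraph that counts up to eight injections in this study.

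**The multiples are ceilings.** This stands in part. Activity is capped at 10 mCi, not fixed; the second smoker set is optional; and the PHNO protocol calls failure after injection rare, so 5.7 is an extreme case. But an unqualified sentence has to hold at permitted activity, and the least exposed group is already at 1.4.

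**The true figures are on the same page.** They are, and the risk section gives them without the background comparison. This limits the harm and keeps the point minor.

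**Stronger readings that the documents do not support**

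- A reader might infer that no choice of dose metric could make the sentence true. For PHNO alone in the NCFHEB protocol that is not so: the total-body figure puts two injections at about 0.21 rad, and the limits printed just before the sentence include whole-body limits. This does not help the PHNO protocol, whose own totals are not on that metric, nor does it cover NCFHEB injections.
- A reader might measure the error in the NCFHEB protocol by its four-scan NCFHEB total or its 3.08 rem annual maximum. The sentence there closes a PHNO-only, per-injection section, and the maximum includes the two PHNO scans of Aim 7, which is closed. Those totals are not the size of this error.
- A reader might infer a dose breach, or that subjects were misinformed. All totals are below 5 rem per year, and the consent pages are not in the file, so neither can be concluded.

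**Conclusion.** The point holds, as a minor one. In the PHNO protocol the comparison with natural background is false as written: at the permitted 10 mCi per injection the ceilings are 0.43, 0.86 and 1.72 rem, or 1.4, 2.9 and 5.7 times one year of background, and no planned participation at that activity falls below it. The conclusion rests on the protocol's own 0.3 rem comparator, its 0.2146 rem per injection, and the plain sense of taking part in the study. A nonsmoker scanned at under about 7 mCi per injection could fall below background, if dose scales with activity.

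In the NCFHEB protocol the sentence is ambiguous in context. It is true for one PHNO injection (0.9 times) and untrue as worded once a subject has one NCFHEB scan (up to 2.1 times).

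The error is one of risk description. The dose totals, compliance with the annual limit, eligibility and the analysis are all unaffected.

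**What to change.** 1. **PHNO protocol, Proposed single study dose limit.** Delete the sentence, or replace it with the ceilings as multiples of one year of background (0.3 rem): nonsmokers up to 0.43 rem as intended (1.4 times) and up to 0.86 rem with repeat scans (2.9 times); smokers up to 0.43 rem for one set (1.4 times), up to 0.86 rem for both sets as intended (2.9 times), and up to 1.72 rem if both sets are fully repeated (5.7 times). Add that all are below 5 rem per year.
2. **NCFHEB protocol, end of the PHNO dosimetry section.** Delete the sentence, or limit it explicitly to one PHNO injection (up to 0.27 rem).
3. **Consent form.** Check that the sentence was not carried over, and correct it if it was.

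The cost is a wording amendment that uses figures already in the protocols. The risk statement becomes less favourable, and nothing in the conduct or analysis of the study changes.
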